### 5.6 BLINDING

At the end of the Baseline Period, subjects who qualify to enter the study will be randomized to receive ZX008 0.2 mg/kg/day, ZX008 0.8 mg/kg/day (maximum dose: 30 mg/day), or placebo and assigned a randomization number by the IVR/IWR system. Once a randomization number is assigned to a subject, the site will record the subject's initials on the corresponding study drug labels. Each bottle will contain the assigned treatment (ZX008 or placebo) and the ZX008 and placebo solutions will be identical.

The blinding scheme instituted for this study will ensure that the volume of study medication taken cannot be associated with the dose group, thus unblinding the study. This is achieved by random assignment of different concentrations of the ZX008 oral solution (1.25 mg/mL, 2.5 mg/mL, and/or 5 mg/mL) by the IVR/IWR system. The IVR/IWR system will instruct site personnel to the volume of oral solution to be administered based on that subject's weight. (Dose will be recalculated by the system once at the midpoint of the study.) During the Titration, Maintenance, Taper/Transition Periods, the subjects and study personnel (investigators, clinical staff, personnel involved in data collection and analysis, the Medical Monitor, and the sponsor) will be blinded to the treatment allocation and to the concentration of ZX008 oral solution. If an investigator feels the blind should be broken, he/she can do so when necessary for treatment decisions. However, the investigator should endeavor to discuss with the Medical Monitor or Sponsor's Medical Representative, if available. The blind should only be broken in the event the knowledge of whether the subject is on active study medication versus placebo is needed to determine course of medical treatment for the event. The subject will be discontinued from the clinical trial upon breaking of the blind and the decision whether the subject can enter the separate open-label extension study will rest with the Sponsor if the subject exited Study 1502 prior to completion.

Confidential Page 48 of 175

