### 5.1 IDENTITY OF INVESTIGATIONAL MEDICINAL PRODUCT

ZX008 drug product is an oral aqueous solution of fenfluramine hydrochloride buffered to pH 5 and provided in concentrations of 1.25 mg/mL, 2.5 mg/mL, and 5 mg/mL. The excipients selected have been approved for use in the formulations of currently marketed drug products and are considered to be safe. The solution formulations will be suitably flavored and colored, and will contain preservatives and a thickening agent. The product is sugar free and is intended to be compatible with a KD.

The formulation will be provided in bottles with tamper-evident, child-resistant caps. The clinical trials material will be supplied in 1 bottle size with nominal fill volume of 120 mL. Matching placebo also will be provided. Doses to be studied include 0.2 mg/kg/day and

0.8 mg/kg/day divided into two daily (BID) doses, up to a maximum of 30 mg/day. An intermediate dose of 0.4 mg/kg/day will be used for titration. The concentration of ZX008 oral solution received by subjects (1.25 mg/mL, 2.5 mg/mL, and/or 5 mg/mL) will be randomized across the 3 available concentrations in order to ensure blinding.

Confidential Page 43 of 175

If the parent/caregiver is unable to administer the full dose due to spillage (eg, dose was spilled during measuring, subject spit dose out during administration), he/she should attempt to give the full dose noting the extra amount used to fulfill the dose. **Care must be taken not to overdose.** If the amount spilled is not known, the parent/caregiver should not give additional medication to avoid potential overdose.

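### Randomly assigned concentrations weaken but do not remove the link between dosing volume and dose group, so Section 5.6 claims more than its mechanism delivers

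*Protocol*

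**What the plan says.** Protocol Section 5.6 (Blinding) makes an absolute statement: the scheme "will ensure that the volume of study medication taken cannot be associated with the dose group". The mechanism follows at once: "This is achieved by random assignment of different concentrations of the ZX008 oral solution", carried out by the IVR/IWR system. Section 5.1 repeats it, saying that the concentration a subject receives "will be randomized across the 3 available concentrations in order to ensure blinding".

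The other facts needed are also in Section 5.1. The solution is "provided in concentrations of 1.25 mg/mL, 2.5 mg/mL, and 5 mg/mL". The active arms are 0.2 mg/kg/day and "0.8 mg/kg/day divided into two daily (BID) doses, up to a maximum of 30 mg/day". For the step between them, "An intermediate dose of 0.4 mg/kg/day will be used for titration".

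Section 5.6 adds that the system tells site staff the volume from the child's weight, that subjects and study personnel do not know the concentration, and that active and placebo solutions are identical. Sections 5.5.2 and 5.5.5 send the reader to Section 5.6 for volumes. No section ties concentration to dose, gives a rule for placebo volumes, or says how volume is handled at the cap.

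**The concern.** If concentration is drawn without regard to dose, a fourfold difference in dose still shows in the volume unless the draws happen to offset it. Not knowing the concentration is no protection. Anyone who holds the protocol and knows the child's weight and volume can test the volume against two doses and three concentrations, and see whether one dose is impossible.

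The main outcomes depend on observers. Convulsive seizures are counted by the caregiver in a diary (Section 7.1.1), and global improvement is rated by caregiver and investigator (Section 7.1.2). Section 3.5 accepts that the principal measure may be regarded as subjective and relies on double-blinding to deal with that. A blinding claim that its own mechanism does not support therefore matters, even if the leak is partial.

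**Working it through.** The protocol states no figure on this point, so there is none to reproduce. The check is to list the volumes.

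**Inputs.** Doses 0.2, 0.4 (titration) and 0.8 mg/kg/day, cap 30 mg/day, concentrations 1.25, 2.5 and 5 mg/mL (Section 5.1); allocation 1:1:1 (Section 5.5.1). Assumption: the three concentrations are equally likely and drawn independently of arm.

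**1. Volumes below the cap.** Volume (mL/kg/day) = dose ÷ concentration.

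| Dose (mg/kg/day) | 1.25 mg/mL | 2.5 mg/mL | 5 mg/mL |
|---|---|---|---|
| 0.2 | 0.16 | 0.08 | 0.04 |
| 0.4 | 0.32 | 0.16 | 0.08 |
| 0.8 | 0.64 | 0.32 | 0.16 |

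At maintenance the 0.2 and 0.8 rows share one value, 0.16. Four of the six dose–concentration pairs, or 2/3 of active subjects, have a volume the other active arm cannot have. At 20 kg the sets are 3.2, 1.6 and 0.8 mL/day against 12.8, 6.4 and 3.2 mL/day.

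**2. How well volume separates the two active doses.** 2/3 × 1 + 1/3 × 1/2 = 0.83, against 0.50 by chance.

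**3. Above the cap.** The cap binds from 30 ÷ 0.8 = 37.5 kg. Beyond that the 0.8 arm takes 24, 12 or 6 mL/day whatever the weight, while the 0.2 arm takes 0.16, 0.08 or 0.04 mL per kg.
- At 50 kg: 8, 4 and 2 against 24, 12 and 6 mL/day. Nothing is shared.
- At 75 kg: 12, 6 and 3 against 24, 12 and 6 mL/day. Two values are shared.
- Above 37.5 kg, exact coincidence occurs only at 75 kg and 150 kg.

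**4. Placebo.** No volume rule is given. Suppose placebo volumes mirror both active arms equally. Below the cap:

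| Volume (mL/kg/day) | P(0.2) | P(0.8) | P(placebo) |
|---|---|---|---|
| 0.04 or 0.08 | 67% | 0% | 33% |
| 0.16 | 33% | 33% | 33% |
| 0.32 or 0.64 | 0% | 67% | 33% |

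The chance of placebo is one third at every volume, so volume says nothing about active against placebo. The best three-arm guess is right 5/9 = 56% of the time, against 33% by chance. If placebo is instead spread evenly over the five volumes, the chance of placebo is 37.5% at the four unshared volumes and 23.1% at 0.16. The result for placebo therefore depends on the missing rule.

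**5. Against a single common concentration.** At 2.5 mg/mL for everyone, the arms would take 0.08 and 0.32 mL/kg/day, a fourfold difference with no overlap. Randomising the concentration improves on that.

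**6. More than one bottle.** Section 5.5.2 starts a new bottle at each titration step, but the protocol does not say whether concentration is redrawn.
- If it is kept, a 0.8 mg/kg/day subject's volume below the cap doubles on Day 5 and again on Day 9, while a 0.2 mg/kg/day subject's stays constant.
- If it is redrawn for the Step 3 bottle and at Days 15, 43 and 71, the chance of 0.16 every time is (1/3)⁴ = 1/81.

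The 2/3 in step 1 is therefore the figure for one maintenance draw.

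**The case against.** Three stronger readings are tempting, and the protocol supports none of them.

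- A reader might infer that randomising the concentrations creates the link, so that the scheme does the opposite of what it claims. Step 5 shows otherwise: it reduces a link that one common concentration would make complete.
- A reader might infer that volume reveals the treatment group. Below the cap it excludes one active dose for two thirds of active subjects. If placebo mirrors both arms, no volume confirms active drug or identifies placebo.
- A reader might infer that the primary comparison, 0.8 mg/kg/day against placebo, is biased. Under mirroring, one third of placebo subjects have a volume that rules out 0.8. Two thirds of the 0.8 arm, but only one third of placebo, have one that rules out 0.2. Expectations could therefore differ between the arms, but the document gives nothing from which to size an effect. The route also rests on an unstated placebo rule and on what caregivers know. Sites hold the protocol; nothing shown says that families are told the set of concentrations, and the handling instructions are not part of the document.

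The best defence of the design is that the system may already pair concentration with dose. The concentrations 1.25, 2.5 and 5 stand in the same ratio as the doses 0.2, 0.4 and 0.8, volume is said to follow weight, and a new bottle starts at each step. That is plausible, and the system specification is not shown. It would move the fault from the design to the description, but Sections 5.1 and 5.6 would then describe the wrong procedure and would still need correcting.

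**Conclusion.** The concern holds in a limited form. The assertion that "the volume of study medication taken cannot be associated with the dose group" does not follow from random assignment of the three concentrations. For a single maintenance draw below the cap, two thirds of active subjects have a volume that excludes the other active dose; above 37.5 kg nearly all do, apart from isolated weights such as 75 kg. What leaks is the exclusion of one active dose. Whether anything leaks about active against placebo depends on a volume rule that the protocol does not state.

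These sizes assume equal, independent draws and the literal wording of Sections 5.1 and 5.6. Any effect on caregiver- or investigator-rated outcomes is possible and unquantified. The text should be corrected in either case, and the assignment rule too if the system really draws at random.

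**What to change.** Have the IVR/IWR pair concentration with dose step: 1.25 mg/mL with 0.2, 2.5 mg/mL with 0.4 and 5 mg/mL with 0.8 mg/kg/day, with placebo at the same volume. Since 0.2/1.25 = 0.4/2.5 = 0.8/5 = 0.16, every arm and step, including taper and transition, takes 0.16 mL/kg/day below the cap. No dose changes. Reword Sections 5.1 and 5.6 to describe pairing and to state the placebo volume rule. If the system already pairs, only the wording needs correcting.

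Pairing does not equalise volume at the 30 mg/day cap. At 50 kg the 0.8 arm would take 30/5 = 6 mL/day and the 0.2 arm 10/1.25 = 8 mL/day. For these subjects let placebo volumes mimic both active arms equally, including the change in volume at Day 9, and limit the Section 5.6 claim to subjects below the cap. The two active doses would remain distinguishable there, and the text should say so. Topping up with placebo solution could close that gap, but it needs extra bottles or mixing and is not clearly cheap.

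Below the cap the cost is system reprogramming and kit assignment with the concentrations already supplied. If pairing is already in place, it is a text amendment only.

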### 5.7 PRIOR AND CONCOMITANT MEDICATION

All medications taken by a subject during the Screening and Baseline Seizure Assessment Periods are regarded as prior therapy and must be documented in the eCRF. Significant medications (eg, antibiotics) taken within 30 days prior to the Screening visit should also be captured. All prior and concomitant AEDs will be collected in the CRF.

All medications taken by a subject after the first administration of IMP are regarded as concomitant medication and must be documented in the eCRF, including over-the-counter medication, herbal and vitamin/supplement preparations. Subjects are required to take at least one concomitant AED during the study. All subjects will continue to receive their existing AED(s) with the same doses throughout the study. Every effort should be made to ensure that the regimen of existing medications remains stable during the study; any changes must be discussed with the sponsor prior to implementation. If a decrease in a concomitant AED is necessary to manage an AE, this must be discussed with the sponsor as soon as possible after implementation if not before implementation. Non-study medications and therapies that are considered necessary for the subject's welfare and will not interfere with the response to the study medication may be given at the discretion of the investigator, informing the Medical Monitor as soon as possible.

It should be noted for any subject receiving hypoglycemic agents, the investigator should consider diabetic medication changes in the setting of weight loss and hypoglycemia.

### 5.7.1 Vagal Nerve Stimulation

Subjects receiving treatment with a VNS may be included as long as the VNS has been in place for at least 6 months prior to entry into the study, the VNS battery is not due for replacement during the study, and stimulation parameters have been kept constant for 4 weeks prior to screening and must remain so throughout the study. The subject's use of VNS will be recorded in the CRF.

# 5.7.2 Ketogenic Diet

Adherence to the KD, or a modified version of KD, is permitted during the study if the dietary habits were initiated more than 4 weeks prior to Screening and remain stable throughout the study. The subject's use of KD will be recorded in the CRF.

### 5.7.3 Rescue Medication for Seizures

The subject's usual or prescribed regimen and frequency of rescue therapy for seizures should be entered into the prior and or concomitant medication sections of the eCRF.

Use of rescue medication is permitted during the study and should be recorded on the eCRF (day, medication[s], dose[s]) and in the diary (day, timeframe associated with seizure episodes). Repeated administrations within the same episode should be recorded separately.

### 5.7.4 Prohibited Concomitant Medication and Food

A list of medications/foods that are to be avoided as ongoing medications or for chronic use if

Confidential Page 49 of 175

initiated during the study from the time of signing the informed consent form (ICF) until the endof-study visit (or early termination) is provided in Appendix 1. If medical necessity requires short-term use of one or more of these medications during the course of the study, please contact the Medical Monitor for approval.

The following concomitant medications are prohibited during the clinical trial:

- AEDs: Phenytoin, carbamazepine, oxcarbazepine, eslicarbazepine, retigabine/ezogabine
- Stiripentol (STP): Subjects must be off STP for a minimum of 21 days prior to the Screening visit.
- Felbamate is prohibited as a concomitant medication unless the subject has been on felbamate for at least 18 months prior to screening, has stable liver function and hematology laboratory tests, and the dose is expected to remain constant throughout the study.
- Drugs that interact with central serotonin, including, but not limited to: imipramine, monoamine oxidase inhibitors, selective serotonin reuptake inhibitors, serotonin-norepinephrine reuptake inhibitors, vortioxetine
- Drugs that increase cardiovascular risk including: atomoxetine and those with noradrenergic reuptake properties (NRIs, SNRIs)
- · Drugs intended to facilitate weight loss
- Other: any form of marijuana, THC and derivatives (including Epidiolex®)

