#### **Duration of Treatment:**

All subjects will receive ZX008 or matching placebo for up to approximately 16 weeks (Titration Period=2 weeks; Maintenance Period=12 weeks; Taper/Transition Period=2 weeks). After completion of the Maintenance Period, eligible subjects may enroll in the open-label extension study, after completion of the transition. Subjects who do not enroll in the open-label extension study will undergo a taper off of study medication (doses will be administered in a blinded fashion similar to the titration, i.e., doses will be decreased in 4-day increments). Follow-up cardiovascular safety assessments, including ECG and ECHO, will be performed 3 to 6 months following the last dose of study medication.

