### 4.5 REMOVAL OF SUBJECTS FROM THERAPY OR ASSESSMENT

While subjects are encouraged to complete all study evaluations, subjects may voluntarily withdraw from the study for any reason at any time. They may be considered withdrawn if they fail to return for visits, or become lost to follow-up for any other reason.

If premature withdrawal occurs for any reason, the investigator must make a genuine effort to determine the primary reason for a subject's premature withdrawal from the study and record this information on the electronic case report form (eCRF). All subjects who withdraw from the study with an ongoing AE must be followed until the event is resolved or deemed stable. If a subject withdraws prematurely after dosing, all data to be collected prior to discharge from the clinical site should be collected at the time of premature discontinuation or at the scheduled discharge.

For subjects who are lost to follow-up (ie, those subjects whose status is unclear because they failed to appear for study visits without stating an intention to withdraw), the investigator should show "due diligence" by documenting in the source documents the steps taken to contact the subject (eg, dates of telephone calls, registered letters).

Subjects must be discontinued from the study for the following reasons, if deemed appropriate by the sponsor or investigator:

1. Development of signs or symptoms indicative of cardiac valvulopathy or regurgitation (mitral, aortic, tricuspid, pulmonary valves), or pulmonary hypertension for which IDSMC, in consultation with the IPCAB, the central cardiac reader, and the investigator believe the benefit of continued participation does not outweigh the risk.

Confidential Page 40 of 175

- 2. Subject is found to have entered the clinical investigation in violation of the protocol.
- 3. Subject requires or starts using the use of an unacceptable or contraindicated concomitant medication.
- 4. Subject's condition changes after entering the clinical investigation so that the subject no longer meets the inclusion criteria or develops any of the exclusion criteria.
- 5. Subject is noncompliant with procedures set forth in the protocol in an ongoing or repeated manner.
- 6. Subject experiences an AE that warrants withdrawal from the clinical investigation.

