- 7. Clinically significant worsening of seizures, judged by investigator or subject/caregiver such that treatment outside of the protocol and other than ZX008 is assumed to be in the subject's best interest. Frequent or increased use of rescue medication may be considered indicative of worsening.
- 8. An "actual suicide attempt" as classified by the Columbia-Suicide Severity Rating Scale (C-SSRS).
- 9. It is the investigator's opinion that it is not in the subject's best interest to continue in the study.
- 10. Subject is found to be pregnant while on study.

Discontinuation decisions will be made at each participating site by the site investigator, except that discontinuations due to development of cardiovascular or cardiopulmonary complications are to be made by the IDMSC with input from the IPCAB and the investigator.

If feasible, the process of discontinuation should be discussed with the Medical Monitor. The decisions regarding the discontinuation of the investigational therapy, whether the study medication should be stopped immediately or tapered should be discussed with the Medical Monitor, but final decisions about the process will remain at the discretion of the site principal investigator.

Subjects who are discontinued from the clinical investigation for any reason will not be replaced.

Subjects may withdraw their consent to participate in the study at any time without having to justify the reason for doing so. The decision to withdraw consent and discontinue participation in the study will not prejudice the subject's future medical treatment in any way. Subjects must be discontinued from receiving ZX008 and/or participating in any further study procedures under the following circumstances:

- The subject or the subject's legally authorized representative wishes to discontinue participation in the study.
- The investigator advises that the subject's safety or well-being could be compromised by further participation in the study.
- The sponsor requests that a subject discontinues participation in the study (eg, due to suspicion of fraud, multiple enrollments in clinical studies, lack of compliance, etc).

Confidential Page 41 of 175

The IDSMC may request that the study be terminated after review of the safety information at any time during the study. The IDMSC will review the data for the development of heart valve disease and pulmonary hypertension as they occur on a case-by-case basis and at regular meetings.

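### Section 5.7.4 ends the Appendix 1 rule on ongoing or chronic medication at Visit 12 (Day 99), although some subjects take ZX008 under this protocol for 8 or 14 more days

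*Protocol*

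**What the plan says.** Section 5.7.4 contains two lists with different periods.

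- **Appendix 1.** The listed drugs are to be avoided as ongoing medication or for chronic use "from the time of signing the informed consent form (ICF) until the endof-study visit (or early termination"). A separate sentence covers short-term need: "If medical necessity requires short-term use of one or more of these medications during the course of the study", the site contacts the Medical Monitor for approval.
- **The list in the section itself.** It opens with "The following concomitant medications are prohibited during the clinical trial" and gives no visit at which the ban ends. It covers named antiepileptics ("AEDs: Phenytoin, carbamazepine, oxcarbazepine, eslicarbazepine, retigabine/ezogabine"), stiripentol, felbamate, and drugs in the central serotonergic, noradrenergic, weight-loss and cannabis groups.

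The heading of Section 6.2.9 and the column heads of Table 1 place End of Study/Early Termination at Visit 12, Study Day 99. Visit 13 (Day 113) has a different name, the post-dose visit (Section 6.3).

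The synopsis (Duration of Treatment) says subjects receive ZX008 or placebo for "up to approximately 16 weeks (Titration Period=2 weeks; Maintenance Period=12 weeks; Taper/Transition Period=2 weeks") and places extension enrolment after the transition. Sections 5.5.4 and 5.5.5, with Tables 4 and 5, set out the dosing after Visit 12.

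**The concern.** A restriction that exists because of what the study drug is should last as long as the study drug does. The protocol works this way elsewhere: contraception runs to 90 days after the last dose (Section 4.4), and adverse event reporting runs to 15 days after the last dose or the last visit, whichever is later (Section 8.4). Section 5.7.4 instead stops at a visit after which blinded dosing goes on, and gives no reason.

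At stake is a small matter of safety and conduct. As worded, a site could start an Appendix 1 drug for chronic use after Visit 12 without breaching that clause while the child is still taking ZX008. For a former placebo subject this would fall in the first two weeks of active treatment. Drugs that stand on both lists also end up with two different end points in one section.

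**Working it through.** **Inputs**

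- End of the Appendix 1 rule: end-of-study visit or early termination (Section 5.7.4), which is Visit 12, Day 99, for completers (Section 6.2.9, Table 1).
- Taper: days 1–4 and 5–8 after completion or early termination (Table 4). The 0.8 mg/kg/day arm takes ZX008 0.4, then 0.2 mg/kg/day. The 0.2 mg/kg/day arm goes to placebo at once, and the placebo arm stays on placebo.
- Transition: days 1–4 and 5–14 after Visit 12 (Table 5). All three arms take ZX008; former placebo subjects start 0.2 mg/kg/day on day 1.
- Titration plus Maintenance: 14 weeks, or 98 days (Section 3.1).

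**Day counts**

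- Taper: (4 − 1 + 1) + (8 − 5 + 1) = 8 days, Study Days 100–107. This reproduces the 8 days stated in Section 5.5.4.
- Transition: (4 − 1 + 1) + (14 − 5 + 1) = 14 days, Study Days 100–113. This agrees with the two-week interval in Section 5.5.5 and with 113 − 99 = 14.

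**ZX008 days after the Appendix 1 rule has ended**

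| Group | Days on ZX008 | Share of planned study-drug days |
|---|---|---|
| Roll-over, all three arms | 14 | 14 / (98 + 14) = 12.5% |
| Taper after completion, 0.8 mg/kg/day | 8 | 8 / (98 + 8) = 7.5% |
| Taper, 0.2 mg/kg/day or placebo | 0 | 0 |

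Section 10.4 numbers the treatment period to Day 99. With 99 days in place of 98 the shares are 14/113 = 12.4% and 8/107 = 7.5%. The shares describe time on study drug, not risk. For an early terminator in the 0.8 mg/kg/day arm the same 8 days follow the day of termination.

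**Which drugs the gap concerns**

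Drugs on the undated list stay barred, so only the rest of Appendix 1 matters. Ritonavir and telaprevir are in Appendix 1 and fit none of the groups on the undated list. Phenobarbital is in Appendix 1 and absent from the list's antiepileptic line. However, exclusion criterion 10 names it as maintenance therapy, and Section 4.5 (item 4) makes developing an exclusion criterion a ground for discontinuation if deemed appropriate. It is therefore largely caught.

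**Primary analysis**

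The T+M period runs from Day 1 to Day 99 (Section 10.4). All days counted above come later, so no primary or key secondary analysis uses them.

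**The case against.** The strongest reply is that other controls already cover these two weeks.

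- Section 5.7 allows new non-study drugs only if they are considered necessary for the subject's welfare and will not interfere with the response to study medication, with the Medical Monitor informed. For existing regimens, "any changes must be discussed with the sponsor prior to implementation". Neither rule ends at Visit 12.
- Section 4.5 lists as a ground for discontinuation: "Subject requires or starts using the use of an unacceptable or contraindicated concomitant medication".
- Section 1.3 says that blocking one elimination pathway is unlikely to change fenfluramine clearance much, with more concern when several are affected together.
- Roll-over subjects must sign the extension consent at Visit 12 or earlier, so the extension protocol may restrict medication from then.
- Early terminators may leave because they need treatment outside the protocol (Section 4.5, item 7), and ending the rule at termination is then reasonable.
- Section 3.6 ties End-of-Study procedures to Section 6.3 as well as 6.2.9, so some sites may already read a later end date.

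Most of this stands and is why the point is minor. It does not close the gap. The Medical Monitor approval route in 5.7.4 is for short-term use, whereas the clause that ends is about chronic use. Section 5.7 leaves a new drug to the investigator's discretion and requires only notification. The extension protocol is not at hand, and enrolment in it comes at Visit 13, after the transition. The cross-reference in 3.6 makes the end date unclear rather than later.

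**Conclusion.** The point holds as a minor one. Section 5.7.4 fixes an end date for the Appendix 1 rule that comes 8 days before the last ZX008 dose for 0.8 mg/kg/day subjects who taper, and 14 days before the end of ZX008 dosing under this protocol for all roll-over subjects. It rests on reading the end-of-study visit as Visit 12, which is the ordinary reading of Section 6.2.9 and Table 1.

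A reader might infer three stronger things that the documents do not support.

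- *That prohibited drugs become freely usable after Visit 12.* The undated list and the controls in Sections 5.7 and 4.5 continue.
- *That most of Appendix 1 lapses.* Subtracting the drugs named on the undated list from Appendix 1 would give a large remainder. That remainder is no measure of size, because the serotonergic group is open-ended and the noradrenergic group is broad, and together they plausibly reach many entries. That ritonavir and telaprevir remain outside rests on ordinary drug class, which is an assumption here.
- *That efficacy results are at risk.* The analysed treatment period has ended by then.

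The documents give no rate at which such drugs would be started in these days, so no risk figure can be given. A chronic start of one of the remaining drugs within 8 to 14 days should be uncommon, and the expected harm is small.

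**What to change.** In Section 5.7.4, change the end of the Appendix 1 period to: *until the last dose of study drug under this protocol (end of taper, or Visit 13 for subjects entering the extension)*.

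Add a route for early terminators who need a listed drug: either the Medical Monitor agrees to its use during the taper, or study drug is stopped at once. Section 4.5 already leaves room for the second option, since "whether the study medication should be stopped immediately or tapered should be discussed with the Medical Monitor" and the site investigator decides.

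The uncovered ZX008 days fall from 8 and 14 to 0. The cost is one sentence, a note to sites, and a restriction that lasts 8 days longer for subjects who taper and 14 days longer for those who roll over. To keep the blind it must apply to tapering subjects in every arm, including those on placebo who gain nothing from it. Sample size, alpha and analyses do not change.
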